4. STUDY POPULATION

a. Population (base)

BCG vaccination 2 to 4 weeks before exposure to SARS-CoV-2 would lead to an optimal immunologic response and best expected clinical effects. As this time point cannot be determined (and may have already passed), participating hospitals will be selected by the study team based on their capability to perform study-related procedures. Currently, rapid tests to evaluate participants previous exposure to COVID19 do not exist, but will emerge in the coming weeks. Blood will be obtained and banked, and serologic status will be evaluated retrospectively.

In-hospital recruitment of hospital personnel will be done in different phases. The selection is based on the likelihood of taking care for patients with SARS-CoV-2 infection and, thus, the risk of SARS-CoV-2 exposure, see figure 3 for an example of recruitment.

Figure 3: Recruitment of subjects for the trial:

b. Inclusion criteria

In order to be eligible to participate in this study, a subject must meet the following criteria:

- Adult (≥ 18 years)
- Male or female
- High risk individual including:
- Health Care Workers (HCW) Personnel working in a healthcare setting, at a hospital, medical center or clinic (veterinary, dental, ophthalmology), or first responders (paramedics, firefighters, or law enforcement).
 1. High risk for severe disease including elderly and those with comorbidities including obesity ($BMI > 25$), elderly (age > 65 years), hypertension, diabetes, reactive airway disease, smokers
 2. Individuals at increased risk of infection because of decreased ability to limit exposure including racial and ethnic minorities, teachers, police, restaurant wait-staff, delivery personnel

c. Exclusion criteria

A potential subject who meets any of the following criteria will be excluded from participation in this study:

- Known allergy to (components of) the BCG vaccine or serious adverse events to prior BCG administration
- Known active or latent *Mycobacterium tuberculosis* or with another mycobacterial species. A history with- or a suspicion of *M. tuberculosis* infection.
- Fever (>38 C) within the past 24 hours
- Pregnancy or planning pregnancy within 30 days of study enrollment
- Breastfeeding
- Suspicion of active viral or bacterial infection
- Any Immunocompromised subjects. This exclusion category comprises: a) subjects with known infection by the human immunodeficiency virus (HIV-1); b) subjects with known neutropenic with less than 1500 neutrophils/mm3; c) subjects with solid organ transplantation; d) subjects with bone marrow transplantation; e) subjects under chemotherapy; f) subjects with primary immunodeficiency; g) known severe lymphopenia with less than 400 lymphocytes/mm3; h) treatment with any anti-cytokine therapies; i) treatment with oral or intravenous steroids defined as daily doses of 10mg prednisone or equivalent for longer than 3 months; j) taking immunosuppressants
- Living with someone who is immunosuppressed or taking immunosuppressive drugs
- Previous documented infection with COVID19
- Active solid or non-solid malignancy or lymphoma within the prior two years
- Direct involvement in the design or the execution of the study
- Not in possession and/or access to use of a smartphone, tablet or computer
- Inability to keep the vaccine site covered in the case of a draining pustule.

Secondary analysis: Disease severity will be based on the level of care required for individuals who test positive for COVID19 as follows: non-hospital-based care; patient hospitalized but no oxygen required; hospitalized and oxygen required; patient treated in intensive care and/or on mechanical ventilation; patient died. Additional WHO criteria for severity include severe pneumonia, respiratory failure, acute respiratory distress syndrome, sepsis and septic shock. Days absent will be self-reported via the CRF. Immunology and epigenetic studies for innate training be implemented as previous discussed[10, 13-15], but in brief, immune cells will be stimulated with non-specific (LPS, mitogen, BCG) and COVID19-specific antigens with immune function measured by ELISA and flow cytometry. Epigenetic studies are discussed in more below.

d. Coordination among participating sites

This is a multi-site study with Houston (BCM, MD Anderson and TAMU) and Los Angeles (Cedars Sinai Medical Center) starting enrollment. Other sites may participate in the United States, but will obtain their own local IRB approval to do so along with executing data use agreements.

All sites will use the same electronic data capture form (REDCap), the same data dictionaries and the same data management plans. Each institution will use independent REDCap “instances” and de-identified data will monthly be exported and be analyzed by the DSMB.

5. TREATMENT OF SUBJECTS

e. Investigational product/treatment

In the United States, only the FDA approved TICE® BCG (for intravesical use) BCG LIVE strain of the BCG (Merck) vaccine or a saline placebo will be administered. This will be given intradermally (0.1mL) in the deltoid area. We are NOT using the BCG Vaccine USP which is also the Tice strain of BCG as it is indicated for the prevention of *Mycobacterium bovis*, at a

different dose, following a different preparation and by means of a different route of administration.

In Houston, randomization will also occur 1:1. (Block randomization discussed below) Placebo vaccine will be 0.1 mL 0.9% NaCl, which is the same amount and color as the intervention.

We remain open to guidance from the FDA and IRBs regarding utilizing additional strains of BCG (eg Russian Strain (Verity), Tokyo Strain (JBL), as they might become available and as necessary). However, we confirm that no other forms of BCG will be administered without IRB and FDA approval. As of 3 April 2020, only the BCG Tice strain will be used in the United States.

4. INVESTIGATIONAL PRODUCT

a. Name and description of investigational product(s)

Participants that are randomized in the active arm will receive BCG vaccine, the FDA-approved TICE® BCG (for intravesical use) BCG LIVE strain in the United States.

b. Summary of findings from non-clinical studies

BCG has been shown to have the ability to train the innate immune system in an in vitro and in vivo setting. eg. when human monocytes are incubated for 24h in vitro with BCG and after a week are re-challenged with another (part of a) pathogen, the cytokine production is increased, compared to non-BCG trained monocytes.[13] BCG also protects in experimental models of viral infections (e.g. influenza) in murine models.¹³

c. Summary of findings from clinical studies

BCG vaccine has been shown to induce training of the innate immune system in vivo, just as heterologous effects of the adaptive immune system (e.g. increased cytokine production by monocytes and lymphocytes of BCG-vaccinated individuals), which is thought to have a protective effect in countries with a high infectious pressure (e.g. most third world countries).^{17,18} After vaccination with BCG, immune cells isolated from healthy individuals react with an increased production of proinflammatory cytokines after stimulation with both specific (MTB) and non-specific (bacterial, viral, fungal) stimuli. Adolescents vaccinated with BCG have shown a 70% decrease in the incidence of respiratory tract infections compared to placebo⁹. In a small Indonesian trial, consecutive BCG vaccination for 3 months reduced the incidence of acute upper tract respiratory infections by 80% (95%CI=22-95%).[7]

d. Summary of known and potential risks and benefits

The potential benefit for subjects randomized to the BCG-arm is that administration of the vaccine could prevent SARS-CoV-2 infection and lower risk on developing severe illness caused by SARS-CoV-2.

Potential risks include only the well-known side effects of both the vaccines. A short summary of the most common side effects includes: discomfort at the injection site, scarring at injection site, fevers, nausea, vomiting. Severe but very uncommon side effects are: neurological symptoms such as injection site abscesses, BCG lymphadenitis, disseminated BCG diseases, osteitis, osteomyelitis, anaphylaxis, formation of keloid/lupoid, suppurative lymphadenitis. A complete list of known side effects can be found in the information product insert.

Subjects that receive the placebo hardly have any potential risks and no benefits. Local hematoma formation can occur at the site of vena puncture.

e. Route of administration and dosage

The TICE® BCG (for intravesical use) BCG LIVE strain will be administered in the upper arm slowly (deltoid area), in about 10 seconds, intradermally 0.1ml of the suspended

vaccine, which accounts for approximately 0.075mg of attenuated *Mycobacterium bovis*. The administered 0.1 mL of reconstituted TICE® BCG (for intravesical use) BCG LIVE strain vaccine is approximately 2×10^5 CFU.

Placebo: Administer at the left upper arm slowly, in about 10 seconds, intradermally 0.1ml of 0.9% NaCl solution.

g. Preparation and labelling of Investigational Product (IP)

Preparation and labelling of the investigational products are performed according to GMP guidelines.

In the United States, TICE® BCG (for intravesical use) BCG LIVE strain will be purchased from Merck and reconstituted and prepared according to the package insert/per the approved prescribing information and will include:

- a) preparation using aseptic technique during reconstitution as stipulated in the prescribing information for TICE BCG (for intravesical use) BCG Live.
- b) that reconstituted TICE® BCG should be kept refrigerated (2–8°C), protected from exposure to direct sunlight, and used within 2 hours of reconstitution.
- c) Unused solution should be discarded after 2 hours.
- d) Intact vials (prior to reconstitution) of TICE BCG should be stored refrigerated, at 2–8°C (36–46°F).

Merck sells and distributes 1×10^8 CFU of TICE® BCG (for intravesical use) BCG LIVE strain in a lyophilized (freeze-dried) powder and this will be reconstituted in 50 mL of preservative-free saline, yielding 2×10^6 CFU/ mL. Administration of 0.1 mL will contain $\sim 2 \times 10^5$ CFU, similar to the quantity of BCG vaccine administered worldwide.

The TICE® BCG (for intravesical use) BCG LIVE strain format of the BCG vaccine available in the United States comes in quantities of 1×10^8 CFU per vial and must be used within 2 hours of reconstitution).

h. Drug accountability

Drug accountability will be done in compliance with each pharmacy per their local standard operating procedures and institutional requirements and dispensed from each local pharmacy's supply.

6. STUDY PARAMETERS/ENDPOINTS

a. Primary study endpoint

Incidence of rt-PCR-confirmed SARS-CoV2 infection following BCG vaccination compared to that following placebo.

b. Secondary study endpoint

In individuals who test positive for Covid-19, the proportion with severe disease following BCG vaccination compared to placebo, as defined by the following necessary care levels: non-hospital care; patient hospitalized but no oxygen required; hospitalized and oxygen required; patient treated in intensive care and/or on mechanical ventilation; patient died.

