Study endpoints: *Primary endpoint:* incidence of SARS-CoV2 infection following BCG vaccination compared to placebo. *Secondary endpoint:* COVID19-related disease severity following BCG vaccination compared to placebo.

Nature and extent of the burden and risks associated with participation, benefit and group relatedness: Based on previous experience and randomized controlled trials in adult and elderly individuals, the risks of BCG vaccination are considered low. The objective of this trial is to evaluate the beneficial effects of BCG vaccination at a population level of high risk health care workers through a mitigated clinical course of SARS-CoV-2 infection. The primary endpoint and the adaptive design with interim analyses facilitate maximum efficiency of the trial, so that results can inform policy making during the ongoing epidemic.

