2. RESEARCH QUESTIONS

Primary Objective:

1. To measure the efficacy of BCG vaccination among HRI and HCW in preventing infection with SARS-CoV2 in the United States.

[figure not shown]
Secondary Objective:

1. To measure the efficacy of BCG vaccination among HRI and HCW in mitigating the severity of Covid-19 disease in the United States.

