3. STUDY DESIGN

A placebo-controlled multi-center adaptive randomized controlled trial, see figure 2 for the logistics of the study.

Figure 2: Study design of the trial

a. Duration of Follow-Up

The duration of follow-up for each participant depends on the interim results of the primary endpoint and the probability of obtaining a result, with a maximum of 168 days. The end of the study is defined as the last patient's last registration in the mobile application. Study participants will collect fingerstick dried blood spot (DBS) samples for serology testing at baseline, weeks 4, 8, 12, 16, 20 and 24. If they develop symptoms, they will be qPCR tested by nasopharyngeal swab, oral swab and/ or fecal swabs.

[figure not shown]

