Participants will complete intermittent surveys via an electronic system every 7 days to assess the presence of any flu-like symptom, including sore throat, fever, headache, malaise, and cough. Note that this is part of routine surveillance for Covid-19 in health workers at the United States site. Consent forms will ask for consent to access this survey information.

Any positive response on the survey will trigger a nasopharyngeal, oral and/ or rectal swab to be collected to test for Covid-19 via rt-PCR

All participants, regardless of survey responses, will have serology for Covid-19 tested at 4 week intervals during the follow-up period (6 months)

If a participant completes the follow-up period and does not test positive for disease, their study participation is complete

If a participant does test positive for disease, their disease status will be ascertained for up to two months or until an outcome is available through one of the following mechanisms: (1) an electronic survey if they are not admitted to the hospital, including questions about the number of days they are ill, daily fever, and other symptoms; or (2) if they are admitted to the hospital, ordinal outcomes for disease severity will be extracted from the hospital's electronic medical records system.

During the first week of follow-up, all participants will actively be asked about any adverse events; thereafter, participants will report unsolicited AEs through the electronic survey. Vaccine related adverse events will be graded using the FDA guidance (<https://www.fda.gov/media/73679/download>) and noted using WHO-recommended Adverse event following Immunization forms (AEFI; <https://vaccine-safety-training.org/classification-of-aefis.html>).

Participants will have the option of donating 12 mL of blood for plasma (serology) and PBMCs for secondary analysis of immune correlates and for future analysis based on covid19-specific IgM and IgG. If they do not donate 12mL of blood, a fingerstick will be required for baseline COVID19 serology.

Dried Blood Spot (DBS): all participants will self-collect DBS samples at week 4, 8, 12, 16, 20 and 24. Envelopes to store the DBS are provided upon enrollment and can be mailed or dropped off at work and picked up by study coordinators.

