10. SAMPLE SIZE AND STATISTICAL ANALYSIS

Data will be reported quantitatively. All analyses will be performed from the intention-to-treat principle. Missing data will be dealt with by multiple imputation using the mice package in R.

a. Sample size calculation

The study in the United States will include at least three sites: Houston (BCM and MD Anderson Cancer Center considered as 'one site' due to proximity), Texas A&M University (TAMU), and Cedars Sinai Medical Center (CSMC). TAMU will enroll 1400 individuals. The proposed enrollment sample size is designed to provide 80% power to detect a 60% vaccine efficacy (a relative risk of 0.4 among the vaccinated). This is based on the observed three-fold decline in respiratory infections in the South Africa adolescent cohort with 80% power and 0.05 type 1 error in a two-tailed test. We expect 5% of study participants to develop symptomatic COVID19 during follow-up, therefore a sample size of 1400, with 700 receiving intervention and 700 receiving placebo. We do not expect significant loss to follow up among HCWs (there has been zero LTF after the first 500 participants). We will plot Kaplan-Meier curves comparing COVID19 disease between the BCG and placebo groups and report hazard ratios and p-values using Cox proportional hazard models. DBS samples will be collected at baseline and weeks 4, 8, 12, 16, 20 and 24 post intervention. PBMCs and plasma donations are optional at baseline, 12 and 24 weeks. If interim analysis identifies a large proportion of participants to be seropositive before intervention, power analysis will be evaluated and an amendment will be submitted if additional participants need to be recruited.

b. Interim analysis

One month after the first 100 participants are enrolled, an interim analysis will be held by the independent statistician of the trial. Data will be exported independently from all sites and then data collated and merged for the interim analysis). The above described statistical analysis will be evaluated as well as safety profile. Enrollment is expected to occur within the first two months of launch. Interim analysis will occur based on study enrollment and three to six interim analysis will occur based on temporal dynamics of enrollment as requested by the DSMB. We will stop the clinical trial early if the p-value of any interim analysis is smaller than the pre-specified type-1 error cutoff. Each interim analyses will be reported to the DSMB.

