c. Primary study parameter(s)

The primary endpoint, development of COVID19 infection, we will use the Cox proportional-hazards model to calculate hazard ratios for the development of Covid-19. This will be reported as the proportion of individuals receiving the intervention who are PCR-positive or seroconvert.

d. Secondary study parameter(s)

Disease severity as discussed above and based on guidelines proposed by the World Health Organization. We will use the Chi square for significance to calculate the risk ratios for the development of severe Covid-19 disease. Disease severity will be based on the level of care required for individuals who test positive for COVID19 as follows: non-hospital-based care; patient hospitalized but no oxygen required; hospitalized and oxygen required; patient treated in intensive care and/or on mechanical ventilation; patient died. Additional WHO criteria for severity include severe pneumonia, respiratory failure, acute respiratory distress syndrome, sepsis and septic shock. Days absent will also be self-reported via the RedCap Research App. Immunology and epigenetic studies for innate training be implemented, but in brief, immune cells will be stimulated with non-specific (LPS, mitogen, BCG) and COVID19-specific antigens with immune function measured by ELISA and flow cytometry. Epigenetic studies are discussed in more detail below.

e. Other study parameters

Continuous baseline characteristics will be reported as mean and standard deviation or median and inter-quartile range, as appropriate. Categorical baseline characteristics will be reported as count and percentage. No statistical testing for baseline characteristics will be performed.

f. Synthesis

In this trial, the BCG vaccine will be used in hospital personnel during the epidemics to prevent infection with the new SARS-CoV-2 virus. The risk of the BCG vaccine is very well known (see product inserts) and only minor local side effects (redness, local pain) are common. The benefits of BCG vaccination based on earlier clinical studies are expected to be a reduction in infection and morbidity of at least 25% compared to unvaccinated individuals, and potentially much higher. These effects are mediated by the capacity of BCG to induce trained immunity and may represent an important tool for protection against SARS-CoV-2 virus infection until a specific effective vaccine is developed.

g. Epigenetic and Immune Corollary Studies

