In a randomized controlled trial, healthy volunteers were vaccinated with placebo or BCG (Bacillus Calmette Guérin) vaccine. These volunteers were injected 14 days latter a trivalent influenza A vaccine. Volunteers previous vaccinated by BCG developed significantly greater titers against hemagglutinin A of the influenza A virus whereas their circulating monocytes were more potent for the production of IFNy.[28]

In another randomized placebo-controlled human challenge study, we found that BCG vaccination induced genome-wide epigenetic reprogramming of monocytes and protected against experimental infection with an attenuated yellow fever virus vaccine strain. Epigenetic reprogramming was accompanied by functional changes indicative of trained immunity.

In clinical studies followed by clinical endpoints, adolescents vaccinated with BCG have shown a 70% decrease in the incidence of respiratory tract infections compared to placebo.⁹ Consecutive BCG vaccination for 3 months in elderly individuals reduced the incidence of acute upper tract respiratory infections by 80% (95%CI=22-95%). BCG vaccine in immunocompetent adult people is considered safe, even in latently infected adults with prior infant BCG vaccination. In a randomized controlled trial that compared revaccination with BCG versus placebo, no serious adverse events were observed in the BCG arm.⁹

c. Can the primary or secondary mechanism be induced in animals and/or in ex-vivo human cell material?

No

d. Selectivity of the mechanism to target tissue in animals and/or human beings

The effect of BCG is restricted to immune cells, with no effects exerted in other tissues.

e. Analysis of potential effect

The effect of BCG on the susceptibility to / or severity of infection with SARS-CoV-2 is unknown. Previous clinical studies with BCG vaccination that have shown a reduction of respiratory tract infection between 30 to 70%. We hypothesize that BCG could alter the clinical course of SARS-CoV-2 infection and demonstrate 60% efficacy in preventing infection with SARS-CoV2. As mentioned previously, based on a previous trial, we expect rare serious adverse events.

f. Pharmacokinetic considerations

BCG is injected intradermally in the skin at the superior region of the arm, and it is known to persist at the site of injection for up to 4 weeks.

g. Study population

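### The primary endpoint is defined in two ways: PCR-confirmed infection in section 6a, PCR-positive or seroconverted in section 10c

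*Combined protocol and SAP*

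**What the plan says.** All references are to the combined protocol and SAP.

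- **Section 6a (primary study endpoint):** "Incidence of rt-PCR-confirmed SARS-CoV2 infection following BCG vaccination compared to that following placebo".
- **Section 10c (primary study parameter):** after naming a Cox model for development of Covid-19, it adds "This will be reported as the proportion of individuals receiving the intervention who are PCR-positive or seroconvert".
- **Summary (study endpoints):** "incidence of SARS-CoV2 infection following BCG vaccination compared to placebo", with no test named.
- **Section 2 (primary objective):** "To measure the efficacy of BCG vaccination among HRI and HCW in preventing infection with SARS-CoV2 in the United States".
- **Section 10a (sample size):** "We expect 5% of study participants to develop symptomatic COVID19 during follow-up, therefore a sample size of 1400". This is a third wording of the event.
- **Section 11e:** the hypothesis is to "demonstrate 60% efficacy in preventing infection with SARS-CoV2", with no infection rate.

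On who is tested, section 3a says "If they develop symptoms, they will be qPCR tested by nasopharyngeal swab, oral swab and/ or fecal swabs", and section 7c says "Any positive response on the survey will trigger a nasopharyngeal, oral and/ or rectal swab". Section 7c also schedules serology for every participant at 4-week intervals, whatever the survey says. Stool swabs from asymptomatic participants are optional and are tested in retrospect for secondary objectives. The last paragraph of section 1 mentions symptoms and serology as examples of how the primary endpoint can be measured.

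**The concern.** The primary endpoint should identify one set of cases. Here two sections, both current text, identify two, and no section ranks them or makes seroconversion a secondary or sensitivity endpoint.

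The difference is not cosmetic. Because PCR mainly follows symptoms and serology does not, 6a counts mainly symptomatic infection and 10c counts infection with or without symptoms. Section 1 itself hypothesises an effect on susceptibility, on severity, or on both. A vaccine that acted mainly on symptoms would look different under the two definitions.

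Three things are at stake:

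- The primary result could be chosen after both have been seen.
- Section 10b stops the trial early on an interim p-value, and that p-value depends on which cases are counted.
- If 10c governs, its power cannot be checked, because no event rate is given for it.

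**Working it through.** **1. Who counts under each definition**

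| Participant | 6a | 10c |
|---|---|---|
| Symptoms, PCR positive | case | case |
| Symptoms, PCR missed or negative, later seroconverts | not a case | case |
| No symptoms, no PCR, seroconverts | not a case | case |

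The 10c cases therefore include all the 6a cases and add others.

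**2. The plan's own sample size**

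Inputs from section 10a: 700 per arm, relative risk 0.4, two-sided alpha 0.05, power 80%, event rate 5% for symptomatic COVID-19. The section does not say whether 5% is the placebo rate or the rate over both arms. With p̄ = (p₁ + p₂)/2, the pooled two-proportion formula is

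n per arm = [1.96·√(2p̄(1−p̄)) + 0.842·√(p₁(1−p₁) + p₂(1−p₂))]² / (p₁ − p₂)²

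- 5% on placebo: 5% v 2% needs 588 per arm (1,176 in total). Power at 700 per arm is 86.4%.
- 5% overall: placebo 0.05/0.7 = 7.14%, BCG 0.4 × 7.14% = 2.86%. This needs 405 per arm (810 in total). Power at 700 per arm is 95.8%.

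Neither reading gives 1,400, but both need fewer, so the stated 80% is met at a single look. The event sized is symptomatic disease, which in practice is close to 6a.

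**3. What each definition would show**

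The documents do not give the share s of infections that are symptomatic, so I assume 80%, 60% and 40% on placebo. I also assume that PCR finds every symptomatic infection and serology every asymptomatic one. Placebo symptomatic cases are 700 × 0.05 = 35, and all placebo infections are 35/s. The p-values are from the chi-square test without continuity correction, applied to expected counts.

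*Scenario A: BCG turns 60% of symptomatic infections asymptomatic and prevents none.*
- 6a: 35 v 35 × 0.4 = 14, p = 0.002.
- 10c: equal arms, about 44 v 44, 58 v 58 or 88 v 88.

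*Scenario B: BCG prevents 60% of symptomatic infections (21 cases) and no asymptomatic ones.* 6a again sees 35 v 14. Under 10c the counts are 35/s v 35/s − 21:

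| s | Cases, placebo v BCG | Efficacy | p | Power |
|---|---|---|---|---|
| 80% | 43.75 v 22.75 | 48% | 0.008 | 75% |
| 60% | 58.3 v 37.3 | 36% | 0.026 | 60% |
| 40% | 87.5 v 66.5 | 24% | 0.073 | 43% |

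The p-value exceeds 0.05 only when s is below about 48%. If 5% is the overall rate, placebo has 50 symptomatic cases and BCG 20. The 10c counts become 62.5 v 32.5, 83.3 v 53.3 and 125 v 95, with p = 0.001, 0.007 and 0.028.

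*Scenario C: 60% efficacy against every infection.* Rates under 10c are 6.25% v 2.5%, 8.33% v 3.33% and 12.5% v 5%. Power is 93%, 98% and 99.9%.

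**The case against.** The best defence is that 10c is only a reporting sentence. The inferential analysis there is the Cox hazard ratio. The sentence about seroconversion says how results will be reported, and it mentions only the intervention group. Section 6a carries the heading of primary endpoint, so it could be taken to govern. I do not think this settles it. The sentence stands directly after the Cox model under the primary parameter, and it is the only case definition given there. The last paragraph of section 1 also brings serology into the measurement of the primary endpoint, which points towards 10c, as does the objective of preventing infection.

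A second objection is that the size rests on assumption. That is fair. The symptomatic shares and the mechanisms come from no section, and test detection is taken as perfect. Scenario B is not robust: if serology found only 70% of asymptomatic infections, the 40% row would be 35 + 36.75 = 71.75 v 14 + 36.75 = 50.75, with p = 0.047. The survey trigger for PCR is also broad, so the real gap may be narrower than modelled. Only scenario A clearly reverses the conclusion.

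A third is that 10c has its own difficulties. Section 10g describes serology as still under development, and seroconversion is dated only to a sampling interval. These bear on which definition to choose, not on whether one must be chosen.

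**Conclusion.** The concern holds. The primary endpoint is defined in two incompatible ways in current text, with a third wording behind the sample size, and no rule says which governs. This must be fixed before an efficacy analysis by arm.

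That conclusion rests on the text and the testing schedule. The modelled p-values only illustrate it. At the extreme, the same trial shows 35 v 14 (p = 0.002) under 6a and no difference under 10c. With uniform 60% efficacy, both definitions would detect the effect with good power. The conflict is therefore not evidence of an underpowered trial. It means that the primary claim is not fixed in advance and that power for the 10c endpoint cannot be verified from the documents.

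**What to change.** Choose one case definition and write it identically in the summary, 6a, 10a and 10c, as a comparison of both arms. Either choice resolves the contradiction.

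- **PCR-positive or seroconversion from a seronegative baseline.** This matches the objective best, with PCR-confirmed symptomatic COVID-19 as a secondary endpoint. It needs a definition of seroconversion, a rule for dating the event in the Cox model, and a statement of how the baseline exclusion in 10g fits the intention-to-treat principle in section 10. It also needs one sampling interval: sections 3a, 7c (text) and 10a give 4 weeks, while section 1 and the follow-up table in 7c give 2. Repeated serology will add some false positives.
- **PCR-confirmed infection.** State that the primary result describes mainly symptomatic infection, and make seroconversion secondary. The cost is a narrower question than the stated objective.

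In 10a, say whether 5% is the placebo or the overall rate, and give the event rate and power for the chosen endpoint.

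Section 10b plans an interim one month after 100 participants, and section 10a already reports follow-up on the first 500. The documents do not say whether results by arm have been seen. The amendment should therefore state whether the choice was made without sight of them.

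The cost is small: wording in four places, one power line and, if serology is included, the rules listed above. Symptom-triggered swabs and scheduled dried blood spots are already in the protocol, so no new sampling is needed.
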